8.1.5. Echocardiogram

A transthoracic echocardiogram will be performed at screening and repeated if clinically significant changes are observed at any time during the study treatment. Images will be obtained in standard views, the time to acquire images should not exceed approximately 45 minutes.

8.1.6. Skin Reactions

Skin reactions will be recorded as AEs. The investigator will assess any skin reactions for their clinical significance and clinically significant skin reactions (as per investigator's judgement) will be reviewed by a dermatologist and if appropriate a skin biopsy will be requested for histological analysis. Further technical details will be provided in the SRM.

8.2. Pharmacokinetics

8.2.1. Blood Sample Collection for Pharmacokinetics

Blood samples for PK analysis of GSK3858279 will be collected at the time points indicated in SoA (Section 1.3). The actual date and time of each blood sample collection will be recorded. The timing of PK samples may be altered and/or PK samples may be obtained at additional time points to ensure thorough PK monitoring. Blood samples of approximately 3 mL for PK analysis of GSK3858279 will be collected. Each PK sample should be collected as close as possible to the planned time relative to the dose (i.e., time zero) administered to the participant on PK days. The actual date and time of each blood sample collection will be recorded.

Details on PK blood sample collection including processing, storage, and shipping procedures will be provided in the SRM.

Samples may be retained for a maximum of 15 years after the last participant completes the study.

8.2.2. Pharmacokinetic Sample Analysis

Serum analysis will be performed under the control of In Vitro/In Vivo Technologies/ Bioanalysis Immunogenicity and Biomarkers (IVIVT/BIB), the details of which will be included in the SRM and CLW as appropriate. Concentrations of GSK3858279 will be determined in serum samples using the currently approved bioanalytical methodology. The bioanalytical site will be detailed in the relevant sample processing documents (e.g. SRM, CLW) and raw data will be archived in the GSK R&D GLP archives. Drug concentration information that may unblind the study will not be reported to investigative sites or blinded personnel until the study has been unblinded.

8.3. Efficacy Assessments

Efficacy assessments will be conducted in Part B of the study only.

8.3.1. Patient Reported Outcomes

All patient reported outcomes (PROs) should be administered before any laboratory assessments and other procedures or consultations to avoid influencing the participants' perception of OA pain.

8.3.2. Daily pain scores

Participants will record pain scores daily (evening time) in a digital tool for the 7 consecutive days preceding dosing (during screening) and then daily from Day 1 to Day 84 (12 weeks). They will assess, over the past 24 hours, both:

- average knee pain intensity in index knee
- worst knee pain intensity in index knee

207804 Protocol Amd 7

Participants will be instructed to complete the pain NRS mately the same time each day. Participants will also record any rescue paracetamol/acetaminophen for knee OA over the past 24 h on a digital tool.

8.3.3. WOMAC osteoarthritis index

[figure not shown]
WOMAC Index 3.1 will be completed by participants on paper questionnaires at time points specified in the SOA (Bellamy, 1988). The questionnaire covers pain, stiffness and function related to osteoarthritis in the index knee over the past 7 days. Participants will respond to each question using an 11-point NRS (0-10), with 0=no

They will be required to take at least 5 minutes to complete the questionnaire.

8.3.7. Joint X-ray

X-ray of the knee will be performed at Screening for eligibility and the radiographs are to be read centrally by the imaging CRO in order to minimise variability of the read. The knee radiographs will be evaluated for exclusion criteria (Section 5.2) and eligibility to confirm a Kellgren Lawrence score ≥2 (see inclusion criterium Section 5.1). Refer to the SRM for details.

8.4. Pharmacodynamics/Biomarkers

Any samples collected during this study may be used to evaluate novel biomarkers related to the pathology of OA or to identify factors that influence the clinical responses and outcomes to dosing with GSK3858279. This approach may also be extended to include the identification of biomarkers associated with AEs.

The timing of sample collections may be adjusted based on emerging PK data or other new information from this study to ensure optimal evaluation of target engagement. Details of the processing, storage and shipping procedures for all samples are provided in the SRM.

Samples may be retained for a maximum of 15 years after the last participant completes the study.

8.4.1. Target Engagement

Serum samples will be collected for the evaluation of the free and total concentrations of CCL17. CCL17 can be detected in circulation and is the biological target for GSK3858279. The intention is to examine the correlation between free and total CCL17 and the effect of administration of GSK3858279 on the free levels of CCL17 in the circulation.

8.5. Immunogenicity Assessments

Serum samples will be collected from all treated participants at pre-dose and various time points post-dosing. The washout samples will be collected at the follow-up visit to minimise interference of circulating drug in the antibody assessments, see SoA (Section 1.3.5). Testing will be performed using the typical tiered approach involving screening, confirmation and titration assays [EMEA, 2017; FDA, 2014], performed by IVIVT, GSK. If sera contain potential anti-GSK3858279 antibodies, they will be confirmed by immune-competition using excess drug, followed by a titration assay.

For each participant, immunogenicity results, including the incidence and titres, will be reported.

8.6. Adverse Events

The definitions of an AE or SAE can be found in Appendix 3.

Consult the Safety Management Plan (SMP: a formal version-controlled document). The SMP describes and serves to *ensure* GSK's overall accountability by maximizing transparency on individual roles and responsibilities for initial and follow up of safety reporting and of the onward reporting responsibilities to regulatory agencies, ethics committees and investigators.

The investigator and any designees are responsible for detecting, documenting, and reporting events that meet the definition of an AE or SAE and remain responsible for following up AEs that are serious, considered related to the study intervention or the study, or that caused the participant to discontinue the study (see Section 7).

8.6.1. Time Period and Frequency for Collecting AE and SAE Information

- All SAEs will be collected from the start of study intervention until the followup visit at the time points specified in the SoA (Section 1.3). However, any
 SAEs assessed as related to study participation (e.g., study intervention,
 protocol-mandated procedures, invasive tests, or change in existing therapy) or
 related to a GSK product will be recorded from the time a participant consents to
 participate in the study.
- All AEs will be collected from the dose of study intervention until the follow-up visit (Section 1.3).

- Medical occurrences that begin before the start of study intervention but after obtaining informed consent will be recorded on the Medical History/Current Medical Conditions section of the CRF (not the AE section).
- All SAEs will be recorded and reported to the sponsor or designee immediately and under no circumstance should this exceed 24 hours, as indicated in Appendix 3. The investigator will submit any updated SAE data to the sponsor within 24 hours of it being available.
- Investigators are not obligated to actively seek AEs or SAEs in former study participants. However, if the investigator learns of any SAE, including a death, at any time after a participant has been discharged from the study, and he/she considers the event to be reasonably related to the study intervention or study participation, the investigator must promptly notify the sponsor.

8.6.2. Method of Detecting AEs and SAEs

- Care will be taken not to introduce bias when detecting AE and/or SAE. Openended and non-leading verbal questioning of the participant is the preferred method to inquire about AE occurrence.
- Participants will be provided with a diary card to collect any changes in health between clinic visits.
- The method of recording, evaluating, and assessing causality of AEs and SAEs and the procedures for completing and transmitting SAE reports are provided in Appendix 3.

8.6.3. Follow-up of AEs and SAEs

After the initial AE/SAE report, the investigator is required to proactively follow each participant at subsequent visits/contacts. All SAEs will be followed until the event is resolved, stabilized, otherwise explained, or the participant is lost to follow-up (as defined in Section 7.4). Further information on follow-up procedures is given in Appendix 3.

8.6.4. Regulatory Reporting Requirements for SAEs

- Prompt notification by the investigator to the sponsor of a SAE is essential so that legal obligations and ethical responsibilities towards the safety of participants and the safety of a study intervention under clinical investigation are met.
- The sponsor has a legal responsibility to notify both the local regulatory authority and other regulatory agencies about the safety of a study intervention under clinical investigation. The sponsor will comply with country-specific regulatory requirements relating to safety reporting to the regulatory authority, Institutional Review Boards (IRB)/Independent Ethics Committees (IEC), and investigators.

- Investigator safety reports must be prepared for suspected unexpected serious adverse reactions (SUSAR) according to local regulatory requirements and sponsor policy and forwarded to investigators as necessary.
- An investigator who receives an investigator safety report describing a SAE or other specific safety information e.g., summary or listing of SAE from the sponsor will review and then file it along with the Investigator's Brochure and will notify the IRB/IEC, if appropriate according to local requirements.

8.6.5. Cardiovascular and Death Events – Part B only

For any cardiovascular events detailed in Appendix 3 and all deaths, whether or not they are considered SAEs, specific Cardiovascular (CV) and Death sections of the CRF will be required to be completed. These sections include questions regarding cardiovascular (including sudden cardiac death) and non-cardiovascular death.

The CV CRFs are presented as queries in response to reporting of certain CV medical dictionary for regulatory activities (MedDRA) terms. The CV information should be recorded in the specific cardiovascular section of the CRF within one week of receipt of a CV Event data query prompting its completion.

The Death CRF is provided immediately after the occurrence or outcome of death is reported. Initial and follow-up reports regarding death must be completed within one week of when the death is reported.

8.6.6. Pregnancy

- The Sponsor will make an effort to collect pregnancy details in female partners of male participants after the dose of study intervention and until 28 weeks after the dose.
- If a pregnancy is reported, the investigator should inform GSK within 24 hours of learning of the pregnancy and should follow the procedures outlined in Appendix 4.
- Abnormal pregnancy outcomes (e.g. spontaneous abortion, fetal death, stillbirth, congenital anomalies, ectopic pregnancy) are considered SAE.

8.7. Treatment of Overdose

For this study, any dose of GSK3858279 greater than the scheduled dose will be considered an overdose.

In the event of an overdose, the investigator should:

- Contact the Medical Monitor immediately.
- Closely monitor the participant for AE/SAE and laboratory abnormalities until the study intervention can no longer be detected systemically (at least 5 half-lives but not less than 90 days). Document the quantity of the excess dose as well as the duration of the overdosing in the CRF.

Decisions regarding dose interruptions or modifications will be made by the investigator in consultation with the Medical Monitor based on the clinical evaluation of the participant.

8.9. Health Economics OR Medical Resource Utilization and Health Economics

Health Economics/Medical Resource Utilization and Health Economics parameters are not evaluated in this study.

9. STATISTICAL CONSIDERATIONS

9.1. Hypotheses

Part A: As the primary objective of the study is safety, there are no formal hypotheses to be evaluated. An assessment of dose proportionality will be conducted for selected pharmacokinetic endpoints (i.e. Cmax, and area under the serum concentration-time curve from zero to time t [AUC(0-t)] or to infinity [AUC(0- ∞]) following single IV dose.

Part B: A comparison between GSK3858279 and Placebo will be made on the pain numerical rating scale. An assessment of the probability of success will also be made comparing GSK3858279 to placebo with respect to the key pain endpoints.

9.2. Sample Size Determination

9.2.1. Sample Size Assumptions

In Part A, at each dose level studied there will be six participants randomised to each of the GSK3858279 treatment groups. For each dose level, there will also be two participants receiving placebo. The sample size is based on feasibility and will be conducted at one centre.

The primary objective of the study is safety, where the number of safety events would be of interest, for example the number who experience a particular adverse event. At each dose level six participants will receive GSK3858279. If 0/6 of a particular safety event in the GSK3858279 group is observed, using a Bayesian approach to determine the credible interval around an observed safety event, we would assume a flat Beta (1,1) prior, and if we were to observe 1 safety event in 6 then the posterior distribution would be Beta (2, 6), where we can be 95% certain that the true probability of the safety event lies between 0.04 and 0.58.

A key secondary objective for the study is to determine the pharmacokinetics of the GSK3858279. However, there have been no studies conducted to date within an appropriate population to assess pharmacokinetic precision estimates with six participants per treatment group.

In Part B, approximately 50 participants (minimum of 20 to a maximum of 80) will be randomised in a 1:1 ratio to receive GSK3858279 or placebo. A positive conclusion will be declared if, given the data, there is at least 90% probability that the difference vs placebo is better than 0. A negative conclusion will be declared if, given the data, there is at least 85% probability that the difference vs placebo is worse than -1.0.

For the primary comparison, assuming a change from baseline in participant's assessment of pain score of -1.5 on placebo, and a standard deviation (SD) of 1.8 (Study NCT02683785 and Lane, 2010), with 50 participants, if the true treatment difference is 0 between the two treatments 82% of trials will be declared negative. If the true treatment difference is 1 then 75% of trials will be declared positive. Under these assumptions, the least significant difference between GSK3858279 and placebo would be -0.85.

If the estimated SD during the trial differs from 1.8, then the sample size may be decreased or increased up to a maximum of 80 total participants to ensure robust conclusions can be drawn.

9.2.2. Sample Size Sensitivity

Part A

A sample size sensitivity analysis has been conducted on the primary endpoint, to investigate different safety event rates. If the number of participants who completed each active dose reduces, then the true incidence rates of safety events that could not be ruled out would change. These changes are outlined below:

N Completing Cohort	Number of a particular safety event observed with GSK3858279	Upper limit of exact 95%CI indicating that a true incidence rate of x% could not be ruled out
6	2	71%
6	3	82%
	0	46%
5	1	64%
	2	78%
	0	52%
4	1	72%
	2	85%

Part B

A sample size sensitivity analysis has been conducted on the primary endpoint in Part B, to investigate a decrease or an increase in SD, current design and prediction highlighted:

N per Arm	SD	Proportion of	Proportion of	Least
		trials correctly	trials correctly	Significant
		deemed	deemed	Difference
		negative if true	negative if true	
		treatment	treatment	
		difference is 0	difference is -1	
14	1.4	80%	73%	-0.87
	1.8	67%	57%	-1.12
	2	61%	52%	-1.24
	2.2	57%	47%	-1.37
	2.4	53%	43%	-1.49
22	1.4	91%	86%	-0.69
	1.8	79%	71%	-0.91
	2	73%	65%	-1.00
	2.2	68%	59%	-1.11
	2.4	64%	54%	-1.21
25	1.4	93%	89%	-0.65
	1.8	82%	75%	-0.85
	2	77%	69%	-0.94
	2.2	72%	63%	-1.04
	2.4	67%	58%	-1.13
32	1.4	97%	94%	-0.58
	1.8	88%	83%	-0.75
	2	83%	76%	-0.83
	2.2	78%	70%	-0.91

N per Arm	SD	Proportion of	Proportion of	Least
		trials correctly	trials correctly	Significant
		deemed	deemed	Difference
		negative if true	negative if true	
		treatment	treatment	
		difference is 0	difference is -1	
	2.4	74%	65%	-1.00
40	1.4	98%	97%	-0.51
	1.8	90%	85%	-0.67
	2	88%	83%	-0.74
	2.2	84%	77%	-0.82
	2.4	80%	72%	-0.89

A sample size of up to 14 per arm (28 total) could be used to maintain the acceptable operating characteristics SD of up to 1.4, and thus provide similar operating characteristics as a trial of 50 participants with and SD of 1.8.

A sample size of up to 40 per arm (80 total) could be used to maintain the acceptable operating characteristics SD of up to 2.4, and thus provide similar operating characteristics as a trial of 50 participants with and SD of 1.8.

If the SD is 1.8 then a total of 22 (44 total) per arm completing Week 8 would still provide acceptable operating characteristics.

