10.9. Appendix 8: Abbreviations and Trademarks

Abbreviations

μg/mL	Micrograms per millilitre
μg*day/mL	Micrograms day per millilitre
ACR	American College of Rheumatology
ADA	Anti-Drug Antibodies
AE	Adverse Event
ALT	Alanine aminotransferase
AST	Aspartate aminotransferase
AUC	Area Under the Curve
AUC(0-t)	Area under the serum concentration-time curve from zero
7100(01)	to time t
AUC(0-∞)	Area under the serum concentration-time curve from zero
7100(0 55)	to infinity
AUC(0-tau)	Area under the serum concentration-time curve over the
7100(0 taa)	dosing interval
BCG	Bacillus Calmette-Guerin
BL	Baseline
BMI	Body Mass Index
BNP	N-terminal pro B-type natriuretic peptide
BUN	Blood urea nitrogen
CFR	Code of Federal Regulation
CI	Confidence Interval
CIOMS	Council for International Organizations of Medical
CIONIS	Sciences
CL	Clearance
Cmax	Maximum observed plasma concentration
CONSORT	Consolidated Standards of Reporting Trials
COVID-19	Coronavirus strain 19
CPPD	Calcium pyrophosphate dihydrate
CRF	Case Report Form
CSR	Clinical study report
CV	Cardiovascular
DEC	Dose Escalation Committee
DEP	Dose Escalation Plan
DNA	Desoxyribonucleic acid
ECG	Electrocardiogram
ЕСНО	Echocardiogram
eCRF	Electronic Case Report Form
eDiary	Electronic diary
FTIH	First time in human
FSH	Follicle Stimulating Hormone
GCP	Good Clinical Practice
GSK	GlaxoSmithKline
	1 *************************************

	T TOLOGOL AITIG T
h	Hours
HBsAg	Hepatitis B Surface Antigen positive
HBcAb	Hepatitis B core antibody
HIPAA	Health Insurance Portability and Accountability Act
HIV	Human Immunodeficiency Virus
HRT	Hormone Replacement Therapy
IB	Investigator's Brochure
ICF	Informed Consent Form
ICH	International Council on Harmonisation of Technical
	Requirements for Registration of Pharmaceuticals for
	Human Use
IDRC	Interim Data Review Committee
IEC	Independent Ethics Committee
IgA	Immunoglobulin A
IgG2	Immunoglobulin G2
IP I	Investigational Product
IRB	Institutional Review Board
ITT	Intent-to-Treat
IV	Intravenous
IVRS	Interactive voice response system
IWRS	Interactive Web Recognition System
Kdeg	Degradation rate
KL	Kellgren and Lawrence
kg	Kilogram
kg/m ²	Kilograms per square meter
LLQ	Lower Limit of Quantification
mAb	Monoclonal Antibody
MABEL	Minimum Anticipated Biological Effect Level
MCH	Mean Corpuscular Hemoglobin
MCV	Mean Corpuscular Volume
MedDRA	Medical dictionary for regulatory activities
mg	Milligram
mg/day	Milligrams per day
mg/kg	Milligrams per kilogram

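### Does the Part A safety precision table need correcting because it is headed as exact 95% confidence limits?

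*Protocol*

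**What the plan says.** Section 9.2.1 of the protocol explains how precision for a Part A safety event is to be read. It does so by "using a Bayesian approach to determine the credible interval around an observed safety event", and states that "we would assume a flat Beta (1,1) prior". The worked case is one event among the six participants on active drug: "if we were to observe 1 safety event in 6 then the posterior distribution would be Beta (2, 6"), from which "we can be 95% certain that the true probability of the safety event lies between 0.04 and 0.58".

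Section 9.2.2 then varies the number completing a cohort and the number of events. Its results column is headed "Upper limit of exact 95%CI indicating that a true incidence rate of x% could not be ruled out". The printed limits are 71% and 82% (2 and 3 events in 6), 46%, 64% and 78% (0, 1 and 2 events in 5), and 52%, 72% and 85% (0, 1 and 2 events in 4). The table mentions no prior or posterior, and the abbreviation list in Appendix 8 expands CI as "Confidence Interval".

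On how the Part A size was chosen, section 9.2.1 says "The sample size is based on feasibility".

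**The concern.** The two subsections appear to name different methods for the same quantity. *Exact*, attached to an interval for a binomial proportion, normally means Clopper-Pearson or a close relative, which is built to give at least nominal frequentist coverage. A flat-prior credible limit carries no such guarantee, and with four to six participants the two differ visibly.

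The table describes what a first-in-human cohort can say about its primary objective, safety. Someone relying on the heading alone would regard event rates above the printed limit as excluded at the exact 95% level when an exact interval would still contain some of them. With 2 events in 4 completers, for example, the printed limit is 85% and the two-sided Clopper-Pearson limit is 93%. If a dose escalation or stopping rule used these limits, that gap would matter.

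**Working it through.** **Inputs.** The (n, x) pairs and printed limits come from the Part A table in section 9.2.2. The prior and the worked example come from section 9.2.1.

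**Step 1: reproduce the worked example.** With a Beta(1,1) prior, x events in n give a Beta(x+1, n−x+1) posterior. For x = 1 and n = 6 this is Beta(2, 6). Its 2.5% and 97.5% points are 0.037 and 0.579, printed as 0.04 and 0.58. Clopper-Pearson for 1 in 6 would be 0.004 to 0.641, so the example is plainly the credible interval.

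**Step 2: apply candidate methods to the table.**

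- Flat-prior credible upper limit: 97.5% point of Beta(x+1, n−x+1).
- Clopper-Pearson two-sided 95% upper limit: 97.5% point of Beta(x+1, n−x).
- Clopper-Pearson one-sided 95% upper limit: 95% point of Beta(x+1, n−x).
- Blaker and Sterne 95% intervals, found by inverting the respective exact tests (the two agree in every row here).

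| n | x | Printed % | Flat prior % | CP two-sided % | CP one-sided % | Blaker, Sterne % |
|---|---|---|---|---|---|---|
| 6 | 2 | 71 | 71.0 | 77.7 | 72.9 | 72.9 |
| 6 | 3 | 82 | 81.6 | 88.2 | 84.7 | 84.7 |
| 5 | 0 | 46 | 45.9 | 52.2 | 45.1 | 50.0 |
| 5 | 1 | 64 | 64.1 | 71.6 | 65.7 | 65.7 |
| 5 | 2 | 78 | 77.7 | 85.3 | 81.1 | 81.1 |
| 4 | 0 | 52 | 52.2 | 60.2 | 52.7 | 52.7 |
| 4 | 1 | 72 | 71.6 | 80.6 | 75.1 | 75.1 |
| 4 | 2 | 85 | 85.3 | 93.2 | 90.2 | 90.2 |

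The zero-event rows can be checked by hand. For 0 in 5, the flat-prior limit is 1 − 0.025^(1/6) = 0.459 and the two-sided Clopper-Pearson limit is 1 − 0.025^(1/5) = 0.522. The table prints 46%.

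**Step 3: compare.** The flat-prior limit rounds to the printed value in all eight rows. None of the exact limits rounds to the printed value in any row. The two-sided Clopper-Pearson limits exceed the printed values by 6.2 to 8.6 points; Blaker and Sterne exceed them by 0.7 to 5.2 points.

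**Step 4: rule out another explanation.** The flat-prior limit for x in n is algebraically the two-sided Clopper-Pearson limit for x in n+1, so the column would also fit exact limits with every N printed one too low. That would need seven participants on active drug in a full cohort, whereas section 4.2 gives six, and section 9.2.1 works through Beta(2, 6) explicitly. The flat prior is the natural source.

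**Step 5: look for uses of the limits.**

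- Section 9.1 sets no formal hypotheses for Part A.
- The halting rules in section 6.7 and the stopping criteria in section 7.1 are counts of participants with events, together with judgement.
- Section 9.4.2 summarises safety descriptively.
- The SAP (sections 2.4 and 8) makes no use of the limits.
- The Amendment 5 entries in protocol Appendix 9 record that Part A was completed in June 2019.

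**The case for a change.** The best argument for acting is that the mismatch is demonstrable, concerns the primary safety objective and costs a few words to put right. The abbreviation list expands CI as a confidence interval, section 9.2.1 writes credible interval in full when it means one, and the heading claims exactness that the figures lack. No common exact method rescues it.

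Part of this stands: the word *exact* is wrong for these numbers. The rest is weaker than it looks. The abbreviation list does not settle how CI is used in this trial. SAP section 7.1.5.1 calls for posterior medians with 95% credible intervals, the efficacy figures listed in SAP Appendix 11 label those same intervals CI, and the SAP's own abbreviation list also expands CI as confidence interval. CI is thus used loosely for both kinds of interval.

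To be misled, a reader would have to pass over the prior, posterior and worked interval printed immediately before the table. Nor do the higher Clopper-Pearson values show the printed ones to be deficient. They answer a different question, and putting them in would overwrite correct figures and break the agreement with section 9.2.1.

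**Conclusion.** This is a clerical slip in one column heading. The eight limits are correct as upper ends of equal-tailed 95% credible intervals under the flat prior the protocol states, with no error in any row. The gap of 6 to 9 points arises only if the heading is taken literally and section 9.2.1 is set aside.

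No change to the plan follows. The sound correction would touch a title and leave every number, analysis and decision as it is, in a planning illustration for a part of the study that has ended. This conclusion rests on two things: that section 9.2.1 states the intended method, which the match in all eight rows and in the 1-in-6 example supports; and that no document outside those reviewed, such as the Dose Escalation Plan, used these limits as a decision threshold. The protocol's own halting and stopping rules give no sign that one did.
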